Appendix C. Pregnancy and Lactation Notification Worksheets

AMGEN [®] Pregnancy Notification Worksheet									
Fax Completed Form to the Country-respective Safety Fax Line select on type in a Foot									
1. Case Administrative inf	ormation								
Protocol/Study Number: 2015025									
Study Design: Interventional Observational (If Observational: Prospective Retrospective)									
2. Contact Information									
Investigator Name Site #									
Phone ()		_)		Email					
Institution									
Address									
3. Subject Information									
Subject ID #	Subject Gen	der: 🗌 Female 🛛	Male Su	bjeot DOB: mm / dd / yyyy					
4. Amgen Product Exposu	re								
Amgen Product	Dose at time of conception	Frequency	Route	Start Date					
Etanercept				mm/dd/yyyy					
Was the Amgen product (or st	udy drug) discontinu	ed? 🗌 Yes 🗌 M	lo lo						
If yes, provide product (or	study drug) stop da	te: mm, kild	, www.	-					
Did the subject withdraw from	the study? 🗌 Yes	No No							
5. Pregnancy information									
Pregnant female's LMP mm	/dd /		known						
Estimated date of delivery mm	/dd /	2007	known 🗆 N	UA.					
If N/A, date of termination (act	ual or planned) mm	/ dd	/ >>>>	_					
Has the pregnant female already d	elivered? 🗌 Yes	No Unknow	vn 🗆 N/A						
If yes, provide date of delivery		d / yyyyy							
Was the Infant healthy? Ves	No Unknow	m ⊡N/A							
If any Adverse Event was experien	ced by the Infant, pr	ovide brief details:							

Form Completed by:	
Print Name:	Title:
Signature:	Date:

Effective Date: March 27, 2011

Page 1 of 1

AMGEN[®]

		-	
	 _		

AMGEN' Lactation Notification Worksheet

Fax Completed Form to the Country-respective Safety Fax Line

	•	ELECT OR TIPE IN		er lak fluttivet				
1. Case Administrative Inf	ormation							
Protocol/Study Number: 20150252								
Study Design: 🗹 Interventional 📋 Observational (If Observational: 🗌 Prospective 🗋 Retrospective)								
2. Contact Information								
Invectigator Name				Site #				
Phone () Fax () Email								
Institution								
Address								
3. Subject Information								
Subject ID #	Subject Date	of Birth: mm	/dd/y	m				
4. Amgen Product Exposu	ITØ							
Amgen Produot	Dose at time of breast feeding	Frequency	Route	Start Date				
Etanercept				mm/dd/yyyy				
Was the Amgen product (or st	udy drug) discontinu	ed? 🗌 Yes 🔲 M	ło					
If yes, provide product (or	study drug) stop da	ite: mm/dd	_/mv	_				
Did the subject withdraw from	the study? 🗌 Yes	No No						
5. Breast Feeding Informa	tion							
-			ie actively tak	ing an Amgen product? Yes No				
If No, provide stop date: m								
Infant date of birth: mm/o								
Infant gender: Female N								
is the infant healthy? Yes								
If any Adverse Event was experien	If any Adverse Event was experienced by the mother or the infant, provide brief details:							
J								

Form Completed by:	
Print Name:	Title:
Signature:	Date:

Effective Date: 03 April 2012, version 2.

Page 1 of 1

# Table of Abbreviations

Abbreviation	Definition	
AE	Adverse Event	
BMI	Body Mass Index	
BSA	Body Surface Area	
CI	Confidence Interval	
CRF	Case Report Form	
CSR	Clinical Study Report	
СТС	Common Toxicity Criteria	
CTCAE	Common Terminology Criteria for Adverse Events	
DLQI	Dermatology Life Quality Index	
DRE	Disease-Related Event	
EOS	End Of Study	
ET	Early Termination	
ICH	International Conference on Harmonization	
IP	Investigational Product	
IPD	Important Protocol Deviation	
LOCF	Last Observation Carried Forward	
MedDRA	Medical Dictionary for Regulatory Activities	
PASI	Psoriasis Area and Severity Index	
PRO	Patient Reported Outcome	
PSI	Psoriasis Symptom Inventory	
PsO	Psoriasis	
SAP	Statistical Analysis Plan	
sPGA	Static Physician's Global Assessment of Psoriasis	
WHODRUG	World Health Organization Drug dictionary	

# 1. Introduction

The purpose of this Statistical Analysis Plan (SAP) is to provide details of the statistical analyses that have been outlined within the protocol for Etanercept Study 20150252 dated 05Feb2016. The scope of this plan includes the final analysis that is planned and will be executed by the Biostatistics department unless otherwise specified.

# 2. Objectives

# 2.1 Primary

To evaluate the efficacy of etanercept at week 12 as measured by a 75% improvement in Psoriasis Area and Severity Index (PASI 75) in adult subjects with moderate to severe plaque psoriasis (PsO) who have failed therapy with apremilast (Otezla®).

# 2.2 Secondary

To evaluate the effect of treatment with etanercept on other efficacy endpoints (PASI, Static Physician's Global Assessment [sPGA], Body Surface Area [BSA]), and patient reported outcomes (PRO), including Psoriasis Symptom Inventory (PSI), Patient Assessment of Treatment Satisfaction, and Dermatology Life Quality Index (DLQI).

# 2.3 Safety

To evaluate the safety and tolerability of etanercept in apremilast failures.

# 3. Study Overview

# 3.1 Study Design

This is a multicenter, open-label, single-arm, phase 4 estimation study in subjects with PsO who have failed apremilast. Approximately 80 subjects will be enrolled in the study, among which at least 10 subjects (and not to exceed 20) will be enrolled for reasons of intolerability to apremilast in the investigator's opinion. The remaining 60 to 70 subjects will be enrolled for reasons of primary or secondary failure to apremilast in the investigator's opinion. The study consists of up to a 45 day screening period, a 24-week treatment period with study visits every 4 weeks, and a 30-day follow-up period for safety. Etanercept dosing will follow the recommended label dosing for patients with plaque PsO.

# 3.2 Sample Size

This study will estimate the proportion of subjects with PsO who achieve a PASI 75 after 12 weeks of treatment with etanercept following failure of treatment with apremilast. In recent etanercept studies, the 12-week PASI 75 response rate for etanercept was ~50 to 60%. The assumed response for a population with failure of treatment with apremilast is

40%. In placebo-controlled phase 3 studies, the PASI 75 placebo response rate was ~5% in subjects with moderate to severe plaque PsO. Therefore, in this single-arm study, if the lower bound of the 95% confidence interval for the proportion of PASI 75 response is above 10%, we can safely conclude that in spite of limitations of a single-arm study (ie, regression to the mean and/or placebo effect), the etanercept effect is real.

The sample size of 80 is more than adequate to achieve a half-width of less than 15% for the 95% confidence interval for the proportion of subjects who achieve a PASI 75 response, assuming a sample proportion of 40% and a lower bound of the confidence interval above 10%.

In a phase 3, randomized, double-blind, placebo-controlled apremilast trial, 17% of subjects reported diarrhea and/or nausea. Of the 80 subjects enrolled, 60 subjects will be enrolled for reasons of failure to achieve adequate response (primary failure) or loss of adequate response (secondary failure) to apremilast in the investigator's opinion. In addition, between 10 and 20 (up to 25%) will be enrolled for reasons of intolerability to apremilast in the investigator's opinion.

- 4. Study Endpoints and Covariates
- 4.1 Study Endpoints
- 4.1.1 Primary Efficacy Endpoint
- PASI 75 at week 12

# 4.1.2 Secondary Efficacy Endpoints

- PASI 75 at all other visits
- PASI 50 and 90 at all visits
- Percent PASI improvement from baseline at all visits
- sPGA of 0 or 1 at all visits
- sPGA of 0, 1, or 2 at all visits
- sPGA at all visits
- One and two grade improvement from baseline in sPGA at all visits
- Percent BSA improvement from baseline at all visits
- PSI total and component scores at all visits
- Patient Assessment of Treatment Satisfaction at week 12 and 24
- DLQI improvement from baseline at week 12 and 24

# 4.1.3 Safety Endpoints

- Adverse events
- Laboratory assessments

# 4.2 Covariates and Subgroups

The following predictors and subgroup analyses may be performed to assess their influence on the primary endpoint:

- Body mass index ( $\leq 35 \text{ kg/m}^2 \text{ or } > 35 \text{ kg/m}^2$ )
- Age (<65, ≥ 65)
- Gender (male vs. female)
- Race (white, non-white)
- Baseline PASI score (≤ median, > median)
- Baseline BSA with psoriasis involvement (%) (≤ median, > median)
- History of psoriatic arthritis (yes, no)
- Baseline sPGA score (3, 4 or 5)
- Reasons for apremilast failure at screening,1) failure to achieve adequate response,
  2) loss of adequate response or 3) intolerability

# 5. Hypotheses and/or Estimations

A formal hypothesis will not be tested in this study. This study will estimate the proportion of subjects with PsO who achieve a PASI 75 after 12 weeks of treatment with etanercept following failure of treatment with apremilast.

# 6. Definitions

#### Adverse Event

In addition to the International Conference on Harmonization (ICH) Guidance definition, an adverse event also includes any occurrence or worsening of a pre-existing medical condition.

#### Age

Age will be collected at baseline.

#### Baseline

The last measurement for the endpoint of interest taken before the first dose of investigational product.

# Body Mass Index (BMI)

A growth measure utilizing both height and weight, as given by the following formula:

weight (kg) squared height (m^2)

#### **Body Surface Area (BSA)**

A measurement of psoriasis involvement, given as the physician's assessment of the proportion of the subject's total body surface area involved with psoriasis.

#### Dermatology Life Quality Index (DLQI)

A skin disease-specific instrument to evaluate health related quality of life ranging from 0 (best possible score) to 30 (worst possible score).

#### **Disease-Related Event (DRE)**

Disease Related Events are events (serious or non-serious) anticipated to occur in the study population due to the underlying disease. Disease related events for the purposes of this study include worsening of the skin symptoms associated with PsO. Such events do not meet the definition of an Adverse Event unless assessed to be more severe than expected for the subject's condition. Events categorized as Disease-Related Events starting on or after first dose of IP as determined by the flag indicating if the AE started prior to the first dose on the Events CRF and up to and including 30 days after the end of IP.

#### **DLQI** Responder

A subject who achieves at least a 5 point improvement from baseline or a 0 (best possible) score at a particular visit.

#### **Duration of Psoriasis**

The number of years between the date of diagnosis and the enrollment date rounded to 1 decimal place, as given by the following formula:

[(year(ENRLDT) - year(DXDT)) \* 12 + ((month(ENRLDT) - month(DXDT))]

12

where ENRLDT=enrollment date; DXDT=date of diagnosis

Note: month(DXDT) is considered to be 0 if month of diagnosis date is missing.

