7.3.3 Physical Examination and Medical History

Physical examination should be completed as per standard of care. Physical examination findings should be recorded on the appropriate CRF (eg, medical history, event). Any clinically significant changes in physical exam throughout the study, per the investigator's opinion, should be recorded on the event CRF.

The Investigator or designee will collect a complete medical and surgical history that started within 5 years prior to enrollment through the first dose of etanercept. In addition to the medical history above, PsO history must date back to the original diagnosis. Medical history will include information on the subject's concurrent medical conditions. Record all findings on the medical history CRF.

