#### **Enrollment Date**

The date of the first dose of investigational product.

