# 10.3 Important Protocol Deviations

Important Protocol Deviations (IPDs) categories are defined by the study team before the first subject's visit and updated during the IPD reviews throughout the study prior to database lock. These definitions of IPD categories, sub-category codes, and descriptions will be used during the course of the study. The final IPD list is used to produce the Summary of IPDs table and the List of Subjects with IPDs Demographic and Baseline Characteristics.

Subject demographic and baseline disease characteristics will be summarized descriptively for all enrolled subjects. Demographic data collection including sex, age, race, height, weight, body mass index and ethnicity will be collected in order to study their possible association with subject safety and treatment effectiveness. The baseline disease summary will include duration of disease, presence of psoriatic arthritis, reasons for apremilast failure, history of tobacco use, history of alcohol use, and the baseline value of each efficacy measure. A summary of prior psoriasis medication use, tabulated by preferred term, will be tabulated also.

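### Setting a missing diagnosis month to 0 dates the diagnosis to the previous December, which overstates psoriasis duration by 1 to 12 months before rounding for each subject lacking the month

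*SAP*

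**What the plan says.** SAP Section 6, under Duration of Psoriasis, defines the variable as "The number of years between the date of diagnosis and the enrollment date rounded to 1 decimal place". The formula takes the difference in calendar years times 12, adds enrolment month minus diagnosis month, and divides by 12. The partial-date rule follows: "Note: month(DXDT) is considered to be 0 if month of diagnosis date is missing". The SAP gives no reason for the value 0 and has no other rule for a partial diagnosis date. Enrolment date is defined separately in Section 6 as "The date of the first dose of investigational product".

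The variable is used once. SAP Section 10.3, in its text on demographic and baseline characteristics, states: "The baseline disease summary will include duration of disease, presence of psoriatic arthritis, reasons for apremilast failure", followed by other items. Protocol Section 7.3.3 sets how far back the history must go: "PsO history must date back to the original diagnosis".

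**The concern.** A rule for a missing month should give a date that the known year permits. Month 0 does not: the formula counts it as one month before January, which is the preceding December. The subject is treated as diagnosed before the year on record, and the unrounded duration exceeds every value the recorded year allows under the same formula.

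The error has one direction, so it does not average out across subjects. The rule is likely to be used at least sometimes, because history must reach back to a diagnosis that may be decades old, and the SAP itself foresees missing months. What is at stake is one row of the baseline table. In a single-arm study, that table is how a reader judges which population the PASI 75 estimate describes.

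**Working it through.** The documents state no figure for this point, so there is none to reproduce. The check applies the SAP formula directly.

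**Inputs**
- Formula, rounding and month-0 rule: SAP Section 6, Duration of Psoriasis.
- Diagnosis months uniform over January to December: an assumption, not in the documents. It is needed only for the averages.
- Share of subjects with a missing month: not in the documents, shown as a range.

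**Error for one subject.** Let Ye and Me be the enrolment year and month, Yd the diagnosis year, and m the true diagnosis month. In months:

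- true duration = 12 × (Ye − Yd) + Me − m
- duration under the rule = 12 × (Ye − Yd) + Me − 0
- error = rule − true = m

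The error is 1 month for a true January, 12 for a true December, and never zero or negative before rounding.

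**Example.** Diagnosis in 2000, month unknown, enrolment in June 2016:
- Rule: (16 × 12 + 6 − 0)/12 = 198/12 = 16.5 years.
- True January: 197/12 = 16.4 years.
- True December: 186/12 = 15.5 years.
- December 1999 entered as a full date: (17 × 12 + 6 − 12)/12 = 198/12 = 16.5 years, identical to the rule.

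**Mean error, diagnosis before the enrolment year.** (1 + 2 + … + 12)/12 = 78/12 = 6.5 months = 0.54 years, with uniform months.

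**Diagnosis in the enrolment year.** The true month cannot exceed the enrolment month, so the largest error is Me months and the mean is (Me + 1)/2. That is 1.0 month for January enrolment, 3.5 for June and 6.5 for December.

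**After rounding to one decimal.** Of the 12 × 12 = 144 pairs of enrolment and diagnosis month, 142 remain overstated, by up to 1.0 year. Two show no change (rounding halves up), both with a true January:
- April enrolment: 196/12 = 16.33 and 195/12 = 16.25 both round to 16.3.
- October enrolment: 202/12 = 16.83 and 201/12 = 16.75 both round to 16.8.

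**Effect on the study mean.** Overstatement = share with missing month × 0.54 years, for diagnoses before the enrolment year:

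| Share missing | Mean duration overstated by (years) |
|---|---|
| 0% | 0 |
| 10% | 0.05 |
| 25% | 0.14 |
| 50% | 0.27 |
| 100% | 0.54 |

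**Other imputed months** (error = m − k for imputed month k, uniform months, before any cap):

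| Imputed month | Range of error (months) | Mean signed error (months) |
|---|---|---|
| 0 (SAP) | +1 to +12 | +6.5 |
| 1 | 0 to +11 | +5.5 |
| 6 | −5 to +6 | +0.5 |
| 7 | −6 to +5 | −0.5 |

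For months 6 and 7 the absolute errors sum to 36 over the twelve months, so the mean absolute error is 36/12 = 3 months.

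**The case against.** The strongest reply is that nothing of consequence depends on the variable. Duration is not an endpoint, an eligibility criterion, or a listed covariate or subgroup (Protocol Section 10.1.3; SAP Sections 4.2 and 10.4.4). It cannot move PASI 75 at week 12, its confidence interval, the analyses by reason for apremilast failure, or any safety table. This stands, and it limits the point to a minor correction.

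A second reply is that any fixed month is a convention. January, which lies inside the recorded year, would still overstate by 5.5 months on average, so only 1 of the 6.5 months comes from leaving that year. The split is correct. But January is at least a date the record allows, whereas month 0 is not, and both parts of the bias go when a mid-year month is used.

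A third is that mid-year imputation leaves real error for individuals. That also stands: the half-month figure is signed bias only.

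Some stronger readings are tempting but unsupported. A reader might infer that every subject's duration is wrong, but subjects with a recorded month are unaffected. A reader might infer that the reported value is always too long, but rounding removes the difference in 2 of 144 pairs. A reader might also take half a year as the error in the study mean. That would need the month to be missing for everyone, and nothing in the documents sets a minimum share above zero.

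**Conclusion.** The rule is wrong as written, and the consequence is small. The direction of the error and its limits of 1 and 12 months follow from the SAP formula alone, before rounding, for each subject with a missing diagnosis month. For diagnoses in the enrolment year the upper limit is the enrolment month. The 6.5-month mean additionally needs uniform diagnosis months and diagnosis before the enrolment year. The study-level effect depends on an unknown share and could be negligible. The fault is confined to the disease-duration row of the baseline summary; the documents give no route from it to an efficacy or safety result.

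**What to change.** In SAP Section 6, Duration of Psoriasis, replace the value 0 with 6 (or 7) for a missing diagnosis month, and add that when diagnosis is in the enrolment year the imputed month may not exceed the enrolment month. The cap is needed because a mid-year month could otherwise fall after enrolment and give a negative duration; month 0 never raised that problem. For diagnoses in earlier years, and with uniform months, average signed bias goes from +6.5 months to +0.5 (month 6) or −0.5 (month 7).

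Reporting the number of subjects with an imputed month beneath the baseline table would let readers see how far the rule matters.

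The cost is a short edit to one SAP definition and the matching derivation code. It needs no new data, no protocol amendment and no change to any efficacy or safety analysis.

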#### End of Study Date

For each subject, this is the date of the End of Study (EOS) visit at week 24 (for subjects who complete the study) or Early Termination (ET) visit (for subjects who withdraw from the study prematurely).

#### **Enrollment Date**

The date of the first dose of investigational product.

#### **First Dose Date**

The date of the first dose of investigational product.

#### Full Analysis Set

Patient population including all enrolled subjects who received at least one dose of investigational product during the study.

#### Improvement from Baseline

The arithmetic difference between the baseline value and a post-baseline value, as given by the following formulas:

For endpoints with higher scores as better clinical results, Improvement from baseline = (Post-baseline Value – Baseline Value)

For endpoints with lower scores as better clinical results, Improvement from baseline = (Baseline Value – Post-baseline Value)

#### **Imputed Value**

A value substituted for a missing value.

#### Infectious Event

An event recorded on the Adverse Events electronic case report form that is coded to the Medical Dictionary for Regulatory Activities (MedDRA) system organ class "Infections and Infestations."

#### **Injection Site Reaction**

An event recorded on the Adverse Events electronic case report form that is coded to the MedDRA high level term of "Injection and Infusion Site Reactions," excluding events with the preferred terms "Injection Site Bruising" and "Injection Site Haemorrhage."

#### Last Dose Date

The date of the last dose of investigational product.

#### Last Observation Carried Forward (LOCF) Imputation

A method of imputation where missing post-baseline efficacy data will be carried forward from the last non-missing post-baseline value for that endpoint.

#### Non-infectious Adverse Event

An event recorded on the Adverse Events electronic case report form that is neither infectious nor an injection site reaction.

#### Non-responder Imputation (NRI)

A method of imputation where missing post-baseline efficacy data will be imputed with a value of zero (for binary endpoints) or with the baseline value (for ordinal and continuous endpoints) to indicate no response.

#### **Patient Satisfaction with Treatment**

A measure of a subject's level of satisfaction with the medication's control of psoriasis, ranging from "very satisfied" to "very dissatisfied."

#### **Patient Years on Drug**

The number of days between the first dose date and the last dose date, inclusive, in a given time period divided by 365.25 and summed over all subjects within a treatment group.

#### Percent Improvement from Baseline

The improvement from baseline divided by baseline and multiplied by 100, as given by the following formula:

(Improvement from Baseline / Baseline) \* 100

Note: If improvement from baseline is 0, the percent improvement from baseline will be set to 0 regardless of the baseline value. If the baseline value is 0, substitute 1 in the denominator for the percent improvement from baseline calculation.

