# 9.5 Outliers

Histograms will be examined to identify outliers in any of the continuous variables used in the analyses. Frequency tables of the categorical data used in the analyses will be examined to identify unexpected values.

Outliers due to data entry errors will be corrected by the study team before data lock. Outliers that are not due to data entry error will be included in the analysis. If it is deemed necessary after the team reviews the output from the planned analyses after data lock, a post-hoc sensitivity analysis excluding subjects with outliers may be performed.

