# 10. Statistical Methods of Analysis

# 10.1 General Principles

The final analysis will be performed after all subjects have completed the week 24 assessments and all data through week 24 and the 30-day safety follow-up have been finalized.

Subject disposition, demographics, and baseline disease characteristics will be summarized descriptively for all subjects.

For efficacy analyses, 95% confidence intervals for estimated responses will be generated as descriptive statistics. All categorical endpoints will be summarized using number and percentage of subjects. In addition to being summarized using number and percentage of subjects, ordinal categorical endpoints will also be summarized using number of observations, mean, standard error, standard deviation, median, 1st quartile, 3rd quartile, minimum, and maximum. All continuous endpoints will be summarized using number of observations, mean, standard error, standard deviation, median, 1st quartile, 3rd quartile, minimum, and maximum.

The primary analysis for all efficacy endpoints will be performed using the full analysis set. Missing values will be imputed using post-baseline last observation carried forward method. A sensitivity analysis for the primary endpoint will be performed using non-responder imputation as described in Section 9.3.2. Sensitivity analyses on all the primary and secondary endpoints will be performed using observed cases as well. In addition, the primary endpoints may be examined using the covariates listed in Section 4.2. Summary statistics will be generated as well as confidence intervals and p-values as appropriate. No multiplicity adjustments will be made for the p-values.

Safety endpoints will be summarized descriptively for all subjects.

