# 10.4.3 Analyses of Patient Reported Outcomes Endpoints

The health related quality of life endpoints in this study include the DLQI, Patient Assessment of Treatment Satisfaction and PSI (See Appendix C). These endpoints are considered secondary and will be analyzed as described in Appendix C as well.

DLQI will be summarized as absolute score, absolute improvement, and percent improvement from baseline for total score and the following subscales: Symptoms and Feelings, Daily Activities, Leisure, Work and School, Personal Relationships, and Treatment. The proportion of DLQI responders, defined as subjects who achieve a 5 point or greater improvement from baseline or 0-score, will be summarized. In addition, the proportion of subjects who achieve a DLQI 0 or 1 score will be summarized.

Patient Assessment of Treatment Satisfaction will be summarized as categorical data.

PSI and component scores will be summarized as absolute score at all visits.

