# 11. Changes From Protocol-specified Analyses

The analyses on all the efficacy and safety endpoints will be repeated by the reasons of apremilast failure at screening: 1) failure to achieve adequate response, 2) loss of adequate response or 3) intolerability. This was not pre-specified in the protocol but will be conducted to assess the potential bias of how the different reasons of apremilast failure would impact the efficacy and safety endpoints in this study.

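### Replacing a zero baseline with 1 makes DLQI percent improvement a non-percentage for any subject who starts at 0 and worsens

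*SAP*

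**What the plan says.** SAP Section 6, under Percent Improvement from Baseline, divides improvement by baseline and multiplies by 100. No change is scored as 0 whatever the baseline. The definition then adds: "If the baseline value is 0, substitute 1 in the denominator for the percent improvement from baseline calculation".

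Section 10.4.3 brings the DLQI under this definition: "DLQI will be summarized as absolute score, absolute improvement, and percent improvement from baseline for total score and the following subscales", followed by six subscales. The listed secondary endpoint in Section 4.1.2 is different: "DLQI improvement from baseline at week 12 and 24". Section 6 defines improvement as "The arithmetic difference between the baseline value and a post-baseline value", so the listed endpoint involves no division. The percent figures are additional summaries.

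Section 10.1 sets the statistics: "All continuous endpoints will be summarized using number of observations, mean, standard error, standard deviation, median", with quartiles, minimum and maximum. On extreme values, Section 9.5 says: "Outliers that are not due to data entry error will be included in the analysis". Exclusion is possible only in a post hoc sensitivity analysis after data lock. Section 11 adds: "The analyses on all the efficacy and safety endpoints will be repeated by the reasons of apremilast failure at screening".

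**The concern.** A percent change from zero is undefined. Putting 1 in the denominator turns the raw point change, times 100, into something that is printed as a percentage of a baseline. On the DLQI the distortion runs one way. The total score goes from 0 (best) to 30 (worst), so a subject at 0 has no room to improve, and every non-zero value the rule produces is negative.

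No entry criterion sets a DLQI minimum. A zero is most plausible on a single subscale, although that is a judgement and not something the documents state. One such subject who worsens by a point or two enters the mean, SD and SE of that table with a value far from the rest. The interpretability of those statistics is at stake, most of all in small subgroups. No claim is made here about p-values.

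**Working it through.** **Where the rule can act.** Protocol Section 4.1.1 requires PASI of at least 10 and BSA of at least 10% at screening and baseline, so an eligible subject cannot have a zero on either. SAP Section 10.4.3 summarises PSI as absolute scores only. That leaves the DLQI percent summaries.

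**What the rule gives.** The DLQI is a lower-is-better scale, so improvement is baseline minus post-baseline.

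- 0 to 0: set to 0%
- 0 to 1: (0 - 1)/1 x 100 = -100%
- 0 to 2: (0 - 2)/1 x 100 = -200%
- 10 to 12 (total score): (10 - 12)/10 x 100 = -20%
- 1 to 3: (1 - 3)/1 x 100 = -200%

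**Effect on a summary.** The plan states no figure to reproduce, and it gives neither the number of zero baselines nor a mean or SD for DLQI percent improvement. All sizes below are therefore illustrations. Let n be the group size, with one zero-baseline subject at value x and the other n - 1 at mean m and SD s. Then:

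- Mean = ((n - 1)m + x)/n
- Variance = ((n - 2)s² + (n - 1)(m - Mean)² + (x - Mean)²)/(n - 1)
- SE = SD/√n

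Take m = 60 and s = 40. For n = 80 and x = -200, the mean is (79 x 60 - 200)/80 = 56.75. The variance is (78 x 1600 + 79 x 3.25² + 256.75²)/79 = 2425, so the SD is 49.2 and the SE 5.5.

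| Group size | No zero baseline (mean / SD) | 0 to 0 | 0 to 1 | 0 to 2 |
|---|---|---|---|---|
| 80 (planned total) | 60 / 40 | 59.3 / 40.3 | 58.0 / 43.6 | 56.8 / 49.2 |
| 20 (largest intolerability group) | 60 / 40 | 57.0 / 41.2 | 52.0 / 52.9 | 47.0 / 70.0 |
| 10 (smallest intolerability group) | 60 / 40 | 54.0 / 42.2 | 44.0 / 63.1 | 34.0 / 90.5 |

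At n = 80 the SE without such a subject is 40/√80 = 4.47. The shifts for 0 to 1 and 0 to 2 are 2.0 and 3.25 points, or 0.45 and 0.73 SE. Each further point of worsening takes another 100/80 = 1.25 points off the mean.

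**Range.** For 0 to 2 at n = 80:

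| m, s | Mean | SD | Mean shift | SD rise |
|---|---|---|---|---|
| 40, 30 | 37.0 | 40.1 | 3.0 | 10.1 |
| 40, 50 | 37.0 | 56.5 | 3.0 | 6.5 |
| 75, 30 | 71.6 | 42.8 | 3.4 | 12.8 |
| 75, 50 | 71.6 | 58.4 | 3.4 | 8.4 |

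**Median.** If the other 79 are roughly normal, the median of the 80 sits near their (40 - 1)/79 = 0.494 quantile, z about -0.016. That gives 60 - 40 x 0.016 = 59.4, so it barely moves.

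**The case against.** The best case for leaving the rule alone has five parts.

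- The rule is explicit and pre-specified, contradicts nothing else in the plan, and touches no listed endpoint. That is true, and it is why the point is minor. Pre-specification makes the value reproducible but does not make it a percentage.
- The instability comes from low baselines in general. A true baseline of 1 that rises to 3 also scores -200%, and removing zeros leaves those subjects in. This stands, and the fix is partial. The difference is that -200% from a baseline of 1 is at least a share of a real baseline.
- Leaving out subjects who can only stay level or worsen nudges the percent mean upward. This also stands, so their number and absolute change have to be shown.
- The sizes are assumed, and the mean shift at n = 80 for a one- or two-point worsening is below one SE. The minimum and quartiles would reveal an extreme value. All true, but Section 9.5 still keeps that value in the mean and SD.
- The small-group figures need the percent summary to be repeated by failure reason. The exploratory rows of SAP Table 1 name only improvement in DLQI. The repeat is read from Section 11, which covers the analyses on all efficacy endpoints; that reading is reasonable but not certain.

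Two further limits apply. The documents give no subscale ranges, so how well a mean of 60 and SD of 40 suit a subscale cannot be checked. The available text of SAP Appendix C is only a heading, so any scoring detail there could not be read.

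**Conclusion.** The concern holds as a minor point of interpretability. For a subject with a zero DLQI baseline who worsens, the SAP's percent improvement is the raw change times 100, and it pulls down the mean and inflates the SD and SE of that table. There is no effect if nobody starts at 0, and little if such subjects stay at 0.

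Under the stated assumptions, one such subject worsening by one or two points lowers the mean by 2 to 3 points in the whole trial. In an intolerability group of 10 to 20, if the summary is repeated there, the mean falls by 8 to 26 points and the SD rises from 40 to between 53 and 90.

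PASI 75 at week 12, absolute DLQI scores and improvement, the DLQI responder proportion and the proportion scoring 0 or 1 do not use this rule.

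**What to change.** In SAP Section 6, replace the substitution with a sentence saying that percent improvement is undefined when the baseline is 0. In Section 10.4.3, add a sentence saying that these subjects are left out of the DLQI percent summaries only, that their number is reported for the total and each subscale, and that their absolute scores and absolute changes are shown. They stay in every absolute DLQI summary on the full analysis set.

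The cost is two sentences and a slightly smaller n in some tables. The percent mean will move up a little because the omitted subjects could not have improved; the count and absolute changes keep any worsening visible. Since low non-zero baselines can still give large negative percentages, absolute improvement should remain the main DLQI summary.
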